10.2.2 TEAEs of special interest

The following TEAEs are considered as TEAEs of special interest:

- autoimmune nephritis
- nephritis
- nephritis allergic
- tubulointerstitial nephritis
- uveitis syndrome
- potential Hy's law

tegorized ar 'ion 10 The TEAEs of special interest, which are captured on the CRF page, will be categorized and presented by SOC, PT and relationship similar to appropriate description in Section 10.2.1.

Clinical laboratory evaluations 10.3

End of Treatment is defined as the last assessment point at which a measured value of the parameter is available during the Treatment Period regardless of scheduled visit or unscheduled visit. The same definition applies hereafter.

10.3.1 Hematology, Biochemistry and Urinalysis parameters

Hematology, biochemistry, and urinalysis parameters are assessed at Visits 1, 3 through 7, EDV, Visit 8, and the Safety Visit and may also be assessed at unscheduled visits.

Observed results as well as change from baseline will be analyzed descriptively for all laboratory parameters by visit and End of Treatment. Incidence of possibly clinically significant treatmentemergent (PCST) results, PCST low value, and PCST high value will be summarized for hematology, blood chemistry and urinalysis parameters, if applicable. The PCST criteria are defined in Section 12.2.1.

A serum pregnancy test is performed at Visit 1 and a urine pregnancy test is performed at Visit 2 and Visit 7/EDV. A urine pregnancy test may also be performed at unscheduled visits. Pregnancy test results will not be summarized but will be provided in a subject data listing.

All summarize of laboratory parameters will only summarize parameters planned based on the protocol; however, both planned and unplanned laboratory parameters will be provided in subject data listings.

10.3.2 **PDILI** laboratory measurements

The number and percentage of subjects with PDILI will be summarized by treatment group. The number and percentage of subjects meeting ALT or AST or both, total bilirubin, alkaline phosphatase criteria and presence of symptoms will be summarized in table.

Listings of subjects with PDILI include alcohol and illicit drug use within past 6 months, the laboratory results for ALT, AST and Total bilirubin, symptoms of hepatitis or hypersensitivity will be provided.

tion

10.4 Vital signs, physical findings, and other observations related to safety

10.4.1 Vital signs

Systolic blood pressure (SBP), diastolic blood pressure (DBP), and pulse rate are assessed for Visits 1 through 7, EDV, Visit 8, and the Safety Visit and may also be assessed at unscheduled visits. Body weight is assessed at all of the same time points except for Visit 2.

Observed values for SBP, DBP, and pulse rate will be summarized for Visits 1 through 7, End of Treatment, Visit 8, and the Safety Visit. Changes from Baseline for SBP, DBP, and pulse rate will be summarized for Visits 4 through 7, End of Treatment, the Visit 8, and the Safety Visit. Same summaries will be provided for body weight.

The number and percentage of subjects with at least one PCST low values, and subjects with at least one PCST high value will be summarized for SBP, DBP, pulse rate, and body weight. Percentages will be relative to the number of subjects with an assessment within each study period. PCST criteria are defined in Section 12.2.2.

Vital signs measurements (absolute values and changes from Baseline) will be listed by visit and timing relative to dosing including changes from Baseline.

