### 7 STUDY TREATMENT(S)

### Description of investigational medicinal product(s) 7.1

Oral film-coated tablets of BRV 25mg, BRV 50mg, and matching PBO tablets will be used in

After an 8-Week Baseline Period and once the subject has fulfilled the eligibility criteria, he/she will be randomized to 50mg/day group, 200mg/day group or PBO group, and enter the double-blind Treatment Period (Visit 3 to Visit 7).

During the Treatment Period, subjects will be treated with BRV 50mg/day, BRV 200mg/day, or the matching PBO tablets in a double-blinded manner. Study medication should be given as 2 equally divided doses administered twice daily except the last week of down-titration. Study medication in the last week of down-titration is given only in the morning. The first intake of newly dispensed study medication should occur in the evening of each visit. Subjects should take IMP according to instructions provided by Investigator.

At the end of the Treatment Period (Visit 7), the subjects entering into the LTFU study or MAP will enter the Transition Period or the subjects not entering into the LTFU study or MAP will enter the Down-Titration Period followed by a Study Drug-Free Period.

The Transition Period (2 weeks) will consist of the following:

- For subjects randomized to BRV 50mg/day group or PBO group, keep same dose as Treatment Period during the Transition Period.
- For subjects randomized to BRV 200mg/day group, the Transition Period will consist of the • following: 2 weeks at BRV 150mg/day.

The Down-Titration Period (4 weeks) will consist of the following:

- For subjects randomized to PBO group, keep PBO during the Down-Titration Period.
- For subjects randomized to BRV 50mg/day group, the Down-Titration Period will consist of the following: 1 week at BRV 25mg/day followed by 3 weeks at PBO.
- For subjects randomized to BRV 200mg/day group, the Down-Titration Period will consist of the following: I week at BRV 150mg/day, 1 week at BRV 100mg/day, 1 week at BRV 50mg/day, followed by 1 week at BRV 25mg/day.

The down-titration procedure needs to be applied in case of early discontinuation or completion without conversion to the LTFU study or MAP.

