10.4.2 Electrocardiograms

ECGs are performed at Visits 1, 4, 5, 7/EDV and Visit 8, and may also be performed at unscheduled visits. An ECG is also performed at the Safety Visit if there is an abnormal finding at Visit 7/EDV.

As for the reported ECG parameters, the observed values and change from baseline will be presented descriptively by treatment group for each scheduled visit and End of Treatment.

The number and percentage of subjects with no abnormality, an abnormal but not clinically significant finding, and a clinically significant finding will be summarized for Visits 1, 4, 5, and 7; End of Treatment; Visit 8 (by Period) and the Safety Visit. Percentages will be relative to the number of subjects with an ECG at each analytical time point. Subjects will be counted at most once within each time point based on the worst observed outcome across all abnormalities at that time point.

Summaries of shift from Baseline to Visits 4, 5, and 7 and End of Treatment will also be provided based on the categories normal and abnormal.

Abnormal ECGs will be listed by subject, visit, and timing relative to dosing.

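### Visit 8 vital-sign and body-weight summaries (and, as far as the SAP says, laboratory summaries) are not split by period, although Visit 8 falls at two very different BRV exposures

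*SAP*

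**What the plan says.** SAP 10.4.1 (Vital signs) names Visit 8 once. Changes from Baseline in SBP, DBP and pulse rate "will be summarized for Visits 4 through 7, End of Treatment, the Visit 8, and the Safety Visit". Observed values are also summarized at an undivided Visit 8, and for weight the text adds "Same summaries will be provided for body weight".

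SAP 10.3.1 asks for descriptive summaries of "laboratory parameters by visit and End of Treatment". It lists Visit 8 among the assessment times but does not say whether the Visit 8 row is divided.

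SAP 10.4.2 (Electrocardiograms) does divide it for the categories of ECG finding, whose time points include "End of Treatment; Visit 8 (by Period) and the Safety Visit". Continuous ECG values in the same section are summarized at each scheduled visit, with no mention of period.

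Protocol Table 5-1 has one Visit 8 column covering Weeks 14 and 16. The dosing text in protocol Section 7 differs by route. For Transition it reads "For subjects randomized to BRV 50mg/day group or PBO group, keep same dose as" in the Treatment Period, while the 200 mg arm takes 150 mg/day for 2 weeks. For Down-Titration the 50 mg arm has "1 week at BRV 25mg/day followed by 3 weeks at PBO", while the 200 mg arm steps through 150, 100, 50 and 25 mg/day, one week each. SAP 3.1 adds that safety summaries are shown for each arm and for both BRV groups combined.

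**The concern.** A by-visit safety row is useful when subjects in a column are at about the same point of treatment. At Visit 8 they are not. Some are continuing BRV before long-term follow-up or the access program; others are finishing a taper. A single mean change for a BRV column then describes neither continued treatment nor withdrawal, and its value depends on how many subjects took each route. Under protocol Section 5.1.1 the route depends partly on whether the investigator expects the subject to benefit from further BRV, so the mix could differ between arms.

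What is at stake is how a reader interprets these rows. Laboratory, vital-sign and weight changes are named as other safety variables, so the rows should be interpretable, but no test or primary conclusion depends on them.

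**Working it through.** **1. Timing.** Protocol 5.1 gives 8 weeks of Baseline, 12 of Treatment, 2 of Transition or 4 of Down-Titration, and 2 drug-free weeks.

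- Visit 8 in Transition: 12 + 2 = Week 14.
- Visit 8 in Down-Titration: 12 + 4 = Week 16.
- Maximum BRV exposure: 12 + 4 = 16 weeks, as stated.
- Total duration: 8 + 12 + 4 + 2 = 26 weeks, as stated.

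The taper also applies after early discontinuation, so for those subjects Visit 8 falls about 4 weeks after the early discontinuation visit (EDV), whatever the study week.

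**2. Daily BRV dose at Visit 8** (protocol Section 7; SAP Tables 3.2 and 3.3).

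| Arm | Transition | End of Down-Titration | Share of randomized dose |
|---|---|---|---|
| BRV 200 mg/day | 150 mg | 25 mg (morning only) | 150/200 = 75% vs 25/200 = 12.5% |
| BRV 50 mg/day | 50 mg | 0 mg (placebo for 3 weeks) | 100% vs 0% |
| Placebo | 0 mg | 0 mg | no mix |

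Protocol 2.2 gives a half-life of about 8 hours in young healthy men. Three weeks is 21 × 24 / 8 = 63 half-lives, so the 50 mg arm carries no BRV at that point. The 200 mg arm is still taking some.

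**3. What a pooled row would average.** Let p be the share of an arm's Visit 8 values that come from Transition. The documents do not give p; the values below are assumed.

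- 200 mg arm: mean dose = 150p + 25(1 − p)
- 50 mg arm: mean dose = 50p

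| Assumed p | 200 mg arm | 50 mg arm | Off BRV in 50 mg arm |
|---|---|---|---|
| 0.90 | 137.5 mg | 45 mg | 10% |
| 0.70 | 112.5 mg | 35 mg | 30% |
| 0.50 | 87.5 mg | 25 mg | 50% |

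The combined BRV column could contain subjects on 150, 50, 25 and 0 mg/day.

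**4. Effect on a mean change, as an upper bound only.** Let q = 1 − p. If an effect has gone completely by the end of the taper, the pooled mean is (1 − q) × the on-drug change, so dilution equals q. For an assumed q of 0.10 to 0.40 that is 10 to 40% in the 50 mg arm. In the 200 mg arm, if the effect is also assumed proportional to dose, dilution is q × (150 − 25)/150, which is 8 to 33%. Any effect that persists, as may happen with weight, makes it smaller.

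**5. Does the SAP resolve this elsewhere?** SAP 3.2.2 assigns every measurement to a study period, so the data for a split will exist. It does not say that the Visit 8 tables are presented by that period. It also lets a subject enter Down-Titration after Transition, starting from the Week 14 Visit 8. Such a subject may have two Visit 8 records, and neither 10.3.1 nor 10.4.1 says which one enters the row.

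**The case against.** The strongest reply is that this is a presentation detail with little consequence. The on-treatment picture comes from Visits 4 to 7 and from End of Treatment, which SAP 3.2.3 and 10.3 restrict to the Treatment Period. Withdrawal has its own Safety Visit row. Vital signs are also listed by visit and timing relative to dosing, and the percentages of possibly clinically significant vital-sign values use subjects assessed within each study period. Protocol 2.4 reports no clinically relevant laboratory or vital-sign changes in earlier Phase 2/3 studies. All of this stands, and it is why the point is minor.

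The reply also rules out several stronger readings that a reader might infer:

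- *That the SAP orders one pooled Visit 8 for laboratory data.* It does not. By visit is silent on the matter, the protocol has separate assessment lists for the two kinds of Visit 8 (8.9 and 8.9.1), and table shells that are not among the documents may already split the row. The single time point is explicit only for vital signs and weight.
- *That both BRV arms mix on-drug and off-drug subjects.* Only the 50 mg arm does. The 200 mg arm mixes 150 and 25 mg/day, and placebo has no dose mix.
- *That the ECG section is a complete model.* Its split covers finding categories, not continuous values, and Table 5-1 schedules a Visit 8 ECG only in Transition. It shows that the wording is available; it is weak evidence of a deliberate omission elsewhere.
- *That attenuation of 10 to 40%, or an imbalance between arms, has been shown.* The documents give no shares by route, overall or by arm, and no effect size to attenuate.

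What the reply does not do is make the Visit 8 row in 10.4.1 interpretable as written.

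**Conclusion.** The point holds as a minor clarification. Followed as written, SAP 10.4.1 gives Visit 8 rows for SBP, DBP, pulse rate and weight that mix 150 with 25 mg/day in the 200 mg arm and 50 with 0 mg/day in the 50 mg arm, with both mixtures in the combined BRV column. SAP 10.3.1 leaves the same question open for laboratory values. The dose contrast follows directly from the documents. The proportions do not, so any percentage is at most an upper bound under assumed shares and full washout, and should not be quoted as a result. It would go too far to say that the trial's safety conclusions are compromised: only descriptive Visit 8 rows are affected, and nothing in the Treatment Period summaries or the efficacy analyses changes.

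**What to change.** In SAP 10.4.1 (stating that it includes body weight) and in 10.3.1, replace the Visit 8 time point with *Visit 8 (by Period: Transition; Down-Titration)*, in line with "Visit 8 (by Period") in 10.4.2. Add two sentences:

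- Visit 8 values after an EDV are shown under Down-Titration. This follows from the period definitions in SAP 3.2.2 but should be said where the tables are specified.
- A subject who down-titrates after Transition and has two Visit 8 records contributes one record to each period's row.

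The cost is a few words in the SAP and one extra row per table. No new data are needed, and no stated sample size, test or figure changes.

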10.4.2 Electrocardiograms

ECGs are performed at Visits 1, 4, 5, 7/EDV and Visit 8, and may also be performed at unscheduled visits. An ECG is also performed at the Safety Visit if there is an abnormal finding at Visit 7/EDV.

As for the reported ECG parameters, the observed values and change from baseline will be presented descriptively by treatment group for each scheduled visit and End of Treatment.

The number and percentage of subjects with no abnormality, an abnormal but not clinically significant finding, and a clinically significant finding will be summarized for Visits 1, 4, 5, and 7; End of Treatment; Visit 8 (by Period) and the Safety Visit. Percentages will be relative to the number of subjects with an ECG at each analytical time point. Subjects will be counted at most once within each time point based on the worst observed outcome across all abnormalities at that time point.

Summaries of shift from Baseline to Visits 4, 5, and 7 and End of Treatment will also be provided based on the categories normal and abnormal.

Abnormal ECGs will be listed by subject, visit, and timing relative to dosing.

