- 17. Subject has history of cerebrovascular accident, including transient ischemic attack, in the last 24 weeks.
- 18. Subject has severe cardiovascular disease or peripheral vascular disease.
- 19. Subject has presence of any sign (clinical or imaging techniques) suggesting rapidly progressing (ie, not expected to stay stable during study participation) brain disorder or brain tumor. Stable arteriovenous malformations, meningiomas, or other benign tumors may be acceptable.
- 20a. Subject has any clinical conditions (eg, bone marrow suppression, severe renal impairment with creatinine clearance [CLcr] <30 ml/min/1.73 m^2) which impair reliable participation in the study or necessitate the use of medication not allowed by protocol.
- 21. Subject has chronic hepatic disease.
- 22. Subject has presence of a terminal illness.
- 23. Subject has presence of a serious infection.
- 24. Subject has history of severe adverse hematologic reaction to any drug.
- 25. Subject has severe disturbance of hemostasis.
- 26. Subject has >2xULN of any of the following: alanine aminotransferase (ALT), aspartate aminotransferase (AST), alkaline phosphatase (ALP), or >ULN total bilirubin (≥1.5xULN total bilirubin if known Gilbert's syndrome).

If subject has elevations only in total bilirubin that are >ULN and <1.5xULN, fractionate bilirubin to identify possible undiagnosed Gilbert's syndrome (ie, direct bilirubin <35%)

For randomized subjects with a Baseline result >ULN for ALT, AST, ALP, or total bilirubin, a Baseline diagnosis and/or the cause of any clinically meaningful elevation must be understood and recorded in the electronic Case Report form (eCRF).

If subject has >ULN ALT, AST, or ALP that does not meet the exclusion limit at screening, repeat the tests, if possible, prior to dosing to ensure there is no further ongoing clinically

relevant increase. In case of a clinically relevant increase, inclusion of the subject must be discussed with the Medical Monitor.

- 27a. Subject has clinically significant laboratory abnormality that may increase the risk 1.21101 associated with study participation or may interfere with the interpretation of study results, according to the judgment of the Investigator.
- 28. Subject has clinically significant ECG abnormalities according to the Investigator.

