# 11.3 Other safety measurements

# 11.3.1 ECG

A standard 12-lead ECG will be performed at time points specified in the schedule of study assessments (Table 5-1).

Baseline (Visit 1) results must be received before Visit 3 randomization. The Investigator will determine whether the results of the ECG are normal or abnormal and assess the clinical significance of any abnormalities.

The original ECG tracing will be signed or initialed and dated by the Investigator and will be retained as part of the source data.

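### The ECG shift table is coded normal/abnormal only, so it cannot show a move from a non-significant abnormal Baseline to a clinically significant ECG

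*SAP*

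**What the plan says.** SAP 10.4.2 plans four ECG outputs.

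- **Numeric summary.** For the reported parameters, "the observed values and change from baseline will be presented descriptively by treatment group", at each scheduled visit and at End of Treatment.
- **Graded table by time point.** "The number and percentage of subjects with no abnormality, an abnormal but not clinically significant finding, and a clinically significant finding will be summarized". It covers Visits 1, 4, 5 and 7, End of Treatment, Visit 8 and the Safety Visit. The counting rule is: "Subjects will be counted at most once within each time point based on the worst observed outcome across all abnormalities". The table is not crossed with Baseline.
- **Shift table.** Baseline against Visits 4, 5 and 7, and then: "End of Treatment will also be provided based on the categories normal and abnormal".
- **Listing.** "Abnormal ECGs will be listed by subject, visit, and timing relative to dosing".

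Four other places bear on the point.

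- Protocol 11.3.1 requires the Investigator to "determine whether the results of the ECG are normal or abnormal and assess the clinical significance of any abnormalities".
- Protocol 6.2, criterion 28, excludes a candidate on this ground: "Subject has clinically significant ECG abnormalities according to the Investigator".
- SAP 2.2.4 names change in ECG findings, as well as in ECG parameters, among the other safety variables.
- SAP 3.2.3 and 10.3 define the End of Treatment value as the last one in the Treatment Period, whether the visit was scheduled or not.

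**The concern.** A shift table shows where subjects went relative to where they began. For ECG findings it is the only categorical summary that does this. With three grades collected and only two used, two different changes become hard to read.

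First, a subject whose Baseline is abnormal but not clinically significant can worsen in grade in only one way, by becoming clinically significant. The two-category table leaves that subject in the abnormal-to-abnormal cell.

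Second, a subject who starts normal and becomes clinically significant falls in the same cell as one who acquires a non-significant finding.

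At stake is the clarity of one descriptive safety table. A reader who wants to know, per arm, how many subjects moved to a clinically significant ECG, and from which starting grade, cannot get the answer from the planned tables.

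**Working it through.** The plan states no figure for this point, so there is none to reproduce. The check is to enumerate the possible transitions and collapse them as the SAP does. Write N for normal, A for abnormal but not clinically significant, and CS for clinically significant.

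**Step 1. Collapse the grades.** Three grades at two times give 3 × 3 = 9 transitions. Exclusion 28 removes the three that start at CS, eligibility deviations aside, which leaves 6.

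| Transition | Cell in the planned shift table |
|---|---|
| N to N | normal / normal |
| N to A | normal / abnormal |
| N to CS | normal / abnormal |
| A to N | abnormal / normal |
| A to A | abnormal / abnormal |
| A to CS | abnormal / abnormal |

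Three of the six are moves to a worse grade: N to A, N to CS and A to CS. The first two share a cell, and the third lies on the diagonal.

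**Step 2. Ask whether the graded table restores the split.** For subjects with both ECGs at a given visit, the planned tables supply:

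- (N to A) + (N to CS) = the normal/abnormal count
- (A to A) + (A to CS) = the abnormal/abnormal count
- (N to CS) + (A to CS) = the CS count in the by-visit table

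That is 3 equations in 4 unknowns. The by-visit count of A adds nothing, because it equals the first two totals minus the third. One quantity stays free. If the by-visit table showed 3 CS subjects, and each of the two shift-table cells held at least 3, the number who came from an abnormal Baseline could be 0, 1, 2 or 3 with the same tables.

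**Step 3. Ask whether the tables count subjects who were ever CS on treatment.** A subject who is CS at Visits 4 and 5 appears in both rows, so the rows cannot be added. If each of Visits 4, 5 and 7 showed 3 CS subjects, the number of distinct subjects could lie anywhere from 3 to 3 × 3 = 9. The End of Treatment row does not settle this, because it takes the last value and not the worst. A CS finding at Visit 4 that has resolved by Visit 7 is absent from it. An unscheduled ECG in mid-treatment enters no named row unless it happens to be the last in the period.

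**Step 4. Illustrate the size.** The documents give 148 subjects per group as the target for the primary efficacy analysis. They give neither the share with an abnormal Baseline ECG nor the number who become CS. Assume 10 to 40% for the first and 3 per arm for the second, with CS arising regardless of Baseline.

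- Abnormal Baseline: 0.10 × 148 ≈ 15, to 0.40 × 148 ≈ 59 subjects per arm.
- CS subjects shown as unchanged: 3 × 0.10 = 0.3, to 3 × 0.40 = 1.2.
- CS subjects merged with non-significant shifts: 3 − 0.3 = 2.7, down to 3 − 1.2 = 1.8.

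Steps 1 to 3 do not depend on these assumptions.

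**The case against.** The case against rests on the rest of SAP 10.4.2, and much of it stands.

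A reader might infer from the shift table that a clinically significant deterioration could go unseen. The documents do not support that. If no eligible subject starts clinically significant, every post-Baseline clinically significant count in the graded table is a new one, shown by arm at each time point. An eligibility deviation at screening would show in the Visit 1 row. The listing would carry both abnormal records of a subject who moved from non-significant to significant, so with few events the split can be recovered by hand. A clinically relevant ECG change could also be reported under the general adverse event definition in Protocol 11.1.1.1, although Protocol 11.3.1 does not expressly require it.

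A reader might also infer that the shift table is the only comparison of subjects with their own Baseline. It is not: numeric change from baseline is planned for the ECG parameters. It is the only categorical comparison.

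The SAP labels no cell of the shift table as worsening, so it does not itself claim that a non-significant new finding is a deterioration. The table supplements the graded one, and ECG is among the other safety variables, not the primary ones. A two-category shift beside a three-category frequency table is a presentation choice, not a contradiction.

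These points settle how much it matters. They do not remove the gap, because recovering a per-arm summary from a subject listing is work that the tables were meant to do. Vital signs are already counted by subjects with at least one flagged value (SAP 10.4.1), and laboratory tests by incidence of flagged results (SAP 10.3.1). The appendix that defines those flags has no ECG criteria, so ECG has no equivalent count.

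**Conclusion.** The point holds as a minor improvement. As coded, the shift table cannot show a change in clinical significance, so it delivers the SAP's own variable of change in ECG findings only in part. Two items are missing from the planned tables: new clinically significant ECGs split by Baseline grade, and the number of subjects per arm with one at any time on treatment, unscheduled ECGs included.

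The conclusion rests on the text of SAP 10.4.2 and on Exclusion 28 having been applied. If a few subjects with a clinically significant Baseline were randomized, the by-visit counts would no longer be purely new findings, and the case for crossing with Baseline would be slightly stronger. The illustrated 0.3 to 1.2 subjects per arm depends wholly on the assumed 10 to 40% and 3 per arm. It should not be read as an estimate for this trial. No hypothesis test, efficacy result or primary safety variable is affected.

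**What to change.** In SAP 10.4.2:

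1. Base the shift tables on the three grades that the section already uses. Rows: Baseline normal, and abnormal but not clinically significant, with a clinically significant row kept for any eligibility deviation. Columns: the same three grades post-Baseline.
2. Add one shift from Baseline to the worst on-treatment ECG, counting each subject once and including unscheduled assessments. State which study periods count as on treatment for this row.

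The first change puts all three moves to a worse grade in separate off-diagonal cells. The second gives the per-arm count of subjects who were ever clinically significant, with their Baseline grade.

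The cost is a revised table shell and one added output. The grading is already needed for the by-visit table, so no new data collection is involved. No testing is added, and there is essentially no downside.
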